• To compare the effects of PIT versus TAU on key psychological measures: suicidal ideation, depression, hopelessness, self-esteem and wellbeing, on the level of harm resulting from self-harm incidents, on the frequency of self-harm thoughts, and on the participant's ACCT status at 8 weeks.

Outcome measures

Primary outcome

	IRAS No: 241606	
WORSHIP III		

The primary outcome is the total number of self-harm incidents in the 8-week period from baseline. We shall also be measuring the total number of self-harm incidents in the 12-weeks from baseline. All self-harm which takes place at a specific time point will count as one incident. For example, if someone cuts themselves on their neck and arm at the same time this will count as one incident; however, if they cut themselves at two different times, in the same day, this will count as two incidents e.g. when there is a gap of 30 minutes between incidents. This approach is consistent with the way incidents of self-harm are recorded on SystmOne and the prison self-harm records e.g. the self-harm incidents log/ACCT/NOMIS/F213.

The primary outcome will be a composite of self-harm incidents derived from self-report, medical databases (SystmOne) and prison databases or paper records (NOMIS; F213 forms, ACCT folders, self-harm incidents logs; daily officer's logs) checked for double entry. This approach was recommended in Borschmann et al (2017) who conclude that relying on one data source for self-harm incidents in incarcerated adults could substantially under-ascertain the actual number of events [23]. Self-harm acts will be recorded on the self-harm incidents logs (participants, prison and SystmOne) and then checked for double entry before they are entered into the CTU database. The date and time of each self-reported incident will be recorded to allow cross-checking with medical and prison records, which record self-harm incidents by date and time, to check for duplication.

Both the intervention group and the control group will be asked to complete a weekly self-harm incidents' log (participants) outlining the number of times they have self-harmed since the last entry. All participants (in control and intervention arm) will be able to self-complete the log, at the end of one week, or complete the log with a research assistant. We will explore with each prison recruiting trusted peers to assist with log completion if the women have low literacy.

Secondary outcomes

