Becks Scale for Suicide Ideation [24]: a 19-item instrument measuring intensity, duration and specificity of thoughts about committing suicide. The BSS has high internal consistency (0.89) and high inter-rater reliability (0.83) [24].

Becks Depression Inventory [25]: a 21-item scale measuring symptoms of depression. The BDI-II has high internal consistency and a retest reliability ranging from 0.73 to 0.96 [26].

Beck Hopelessness Scale [27]: a 20-item self-report inventory designed to measure three major aspects of hopelessness: feelings about future, loss of motivation and expectations. The BHS has high concurrent validity (.86) and high reliability ($\alpha = .91$) [27].

Rosenberg Self-Esteem Scale [28]: a 10-item Likert scale with items answered on a four-point scale – from strongly agree to strongly disagree. The scale measures self-esteem and has been used in prison research [29]. Internal consistency ranges from .77 to .88 and test-retest reliability ranges from .82 to .85 [29].

Warwick-Edinburgh Mental Well-Being Scale [30]: a 14-item scale of mental well-being covering subjective well-being and psychological functioning, in which all items are worded positively and address aspects of positive mental health. The WEMWBS has high internal consistency (α = .91) and test-retest reliability (0.83) [30].

ACCT: The Assessment, Care in Custody and Teamwork (ACCT) process is a prison-based system for self-harm monitoring and management. We will record whether the participant is taking part in the ACCT process at 8-weeks and at 12 weeks.

Exploratory outcomes

	IRAS No: 241606
WORSHIP III	

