Level of harm resulting from self-harm incidents: Following Hawton et al [1], the level of harm resulting from self-harm incidents will be measured as follows: incidents will be classified as resulting in a high level of harm when they involve loss of life, resuscitation in prison, an overnight stay in hospital, external hospitalisation on life support or a combination of these. A medium level of harm will be defined as external hospitalisation other than life support (NOT an overnight stay) and a low level of harm will be defined as any episode not needing resuscitation or external hospitalisation. The level of harm will be recorded by the individual on the self-harm incidents' log (participants), for non-fatal incidents, and cross referenced with data recorded in the self-harm incidents logs (prison and SystmOne). Any deaths will be reported in the self-harm incidents logs (prison and SystmOne). For each participant, we shall calculate an average level of harm across all incidents.

Self-harm thoughts: Self-harm thoughts will be measured in a weekly diary on a Likert Scale. Women will be asked to report how often they have had thoughts of self-harm since the due date for their last weekly diary (not at all; almost never; sometimes; almost always; all the time).

Objectives	Outcome Measures	Timepoint(s) of evaluation of this outcome measure (if applicable)
Primary Objective To compare the effect of modified PIT versus TAU on incidents of self-harm	Self-harm incidents (composite of self-report and prison/healthcare records)	8-week post baseline (primary outcome); 12-weeks post baseline
Secondary/Exploratory Objectives To compare the effects of PIT versus TAU on key psychological measures: suicidal ideation, depression, hopelessness, self-esteem and wellbeing, on the level of harm resulting from self-harm incidents, on the frequency of self-harm thoughts, and on the participant's ACCT status.	Becks Scale for Suicide Ideation Becks Depression Inventory Beck Hopelessness Scale Rosenberg Self-Esteem Scale Warwick-Edinburgh Mental Well-Being Scale Prison ACCT documents Self-reported self-harm thoughts Likert scale (in the diary) Self-reported level of harm resulting from self-harm incidents cross referenced with prison records and SystmOne	8-weeks post baseline; 12- weeks post baseline
Process Evaluation	Therapy Satisfaction Questionnaire	10 weeks post baseline

Table of outcomes.

TRIAL DESIGN

Pragmatic randomised controlled trial

	IRAS No: 241606	

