Multicentre: Women's prisons in England/Wales. 7-9 prisons will be recruitment and treatment sites and 3-5 additional prisons will be follow up sites only. A list of the participating sites can be found in the Master file and Site files. Research in prisons requires HMPPS National Research Committee approval (https://www.gov.uk/government/organisations/her-majestys-prison-and-probation-

service/about/research) and Governor approval. We have provisional agreement from study prisons and HMPPS have agreed to facilitate access.

PARTICIPANT ELIGIBILITY CRITERIA

Trial Participants – Women in Prison

Inclusion criteria (as piloted in WORSHIP I and II)

- The participant is a remand or sentenced woman in prison who is on an ACCT currently or has been on an ACCT in the last 8 weeks. ACCT refers to the Assessment Care in Custody and Teamwork process which is used in prisons for self-harm monitoring and management. The ACCT process is started when women are at risk and often experiencing thoughts of self-harm. It is designed to target people who are at risk of self-harm repetition.
- The participant is a woman in prison who has self-harmed in the last month.
- The participant is 18 years or over. The intervention has been piloted with adults as women under 18 may have different needs.
- The participant has been screened for date of release or trial and has a minimum of 8 weeks left in prison, at baseline, to complete the intervention sessions

Exclusion criteria

- The participant is currently involved in another psychological intervention in the prison establishment which has aims that overlap with PIT, e.g. it is designed to address their distress or self-harm via a talking therapy approach or they are booked to start an overlapping therapy during the 12-week study period
- The participant lacks capacity to consent to research participation. This assessment will be made by experienced researchers in collaboration with prison staff and healthcare staff and will be based on the principles behind the Mental Capacity Act (2005).
- The participant is too distressed/unwell to participate in research. This decision will be based on consultation with Safer Custody/healthcare staff and their case manager and psychiatrist (if they have one). For example, women who are at a very high risk of suicide may be excluded as they will be too distressed to engage effectively with therapy.

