During the study period (12-weeks), all participants will complete a weekly diary and the Self-Harm Incidents' Log (Participants), alone, with a trusted peer, or with the research assistant. They will also complete the Concomitant Therapies Form with a research assistant. The diary will include any thoughts of self-harm that have occurred since the last diary date, and any life events which have influenced their self-harm (including the time spent outside their cell). The Self-Harm Incidents' Log (Participants) will include incidents of self-harm in the last week and the severity of the incidents of self-harm. The Concomitant Therapies Form will contain information on any new therapy that has been started during the study period. Information in the Self-Harm Incidents' Log (Participants), will be cross checked with information from prison records (e.g. self-harm incidents databases) and SystmOne using the relevant Self-Harm Incidents' Logs. Concomitant Medications will be recorded from SystmOne on the concomitant therapies this information will be checked using the relevant details for the concomitant therapies this information will be checked using the relevant prison or healthcare databases. We shall also collect the dates and duration of time that women spent on a basic regime during the intervention period from NOMIS on the Basic Regime Data Collection Form.

At 8-weeks and 12-weeks, all participants will complete the secondary outcome measures (BSS; BDI-II; BHS; RSE; WEMWBS) and the health related quality of life scales (EQ-5D-5L; SF-12) and we shall record on the ACCT Status Form whether or not they are participating in the ACCT process.

If a participant is transferred part way through the research, we will seek permission from the receiving prison to complete the ongoing measures (e.g. concomitant medication) and the follow up measures. This will require local access to prison and healthcare databases. We will seek permission from the

WORSHIP III	IRAS No: 241606

participant in the consent process to contact their probation office / CRC for help to locate the women to try to complete ongoing and follow up measures.

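### ACCT status exists only in custody but is recorded to week 12 in women required to have only 8 weeks left in prison, with no listed baseline value and no stated code for women who have been released

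*Protocol*

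**What the plan says.** The Secondary outcomes section says that the ACCT "process is a prison-based system for self-harm monitoring and management" and sets the assessment: "We will record whether the participant is taking part in the ACCT process at 8-weeks and at 12 weeks". Trial procedures applies this to all participants at both visits: "we shall record on the ACCT Status Form whether or not they are participating in the ACCT process".

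The time points differ between sections. The Secondary/Exploratory objectives end with "and on the participant's ACCT status at 8 weeks". The Table of outcomes gives "8-weeks post baseline; 12- weeks post baseline" for the row that contains the ACCT documents.

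Under Inclusion criteria, a participant is screened for release or trial date and "has a minimum of 8 weeks left in prison, at baseline, to complete the intervention sessions". The ACCT criterion admits a woman "who is on an ACCT currently or has been on an ACCT in the last 8 weeks". Remand as well as sentenced women are eligible.

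The Consent section foresees early release and limits the transfer hold to the intervention period. The Payment section provides for follow-up of released women in the community.

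Neither Trial procedures nor Baseline data lists ACCT status at entry; both name the five psychological scales. The baseline summary table does not carry it either.

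**The concern.** A woman whose release falls in weeks 9 to 12 meets the entry criteria, and a remand woman may leave sooner. Once out, she cannot be on an ACCT. Her status is then undefined rather than unobserved, but a yes/no record has one literally true answer for her, and it is the same answer as for a woman whose ACCT was closed. If the two are pooled, the 12-week comparison mixes an effect on ACCT status with the rate of release.

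The entry criterion adds a second problem. Some women start with an open ACCT and others with one closed up to 8 weeks before. Without a variable that separates them, a woman not on an ACCT at follow-up may have had hers closed during the trial or may have had none open at the start.

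**Working it through.** The protocol gives no ACCT proportions and no release rates, so there is no stated figure on this point to reproduce. The one planned number used is 132 per arm: 105 / (1 − 0.20) = 131.25, rounded up to 132, which agrees with the Sample size calculation. Everything else below is assumed.

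**Dilution with equal release.** Let p be the proportion on an ACCT among women in custody and r the share released. If release is recorded as not participating, the recorded proportion is p × (1 − r). The recorded difference is therefore the in-custody difference × (1 − r), and the risk ratio does not change.

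Power is for an unadjusted two-sided 5% comparison with n per arm, d the difference and p̄ the mean proportion:

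Φ{[d − 1.96 √(2p̄(1 − p̄)/n)] / √([p₁(1 − p₁) + p₂(1 − p₂)]/n)}

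Example at r = 0.20: the recorded proportions are 0.40 and 0.28, so d = 0.12 and p̄ = 0.34. The numerator is 0.12 − 1.96 × √(2 × 0.34 × 0.66/132) = 0.12 − 0.1143 = 0.0057. The denominator is √((0.40 × 0.60 + 0.28 × 0.72)/132) = 0.0578. The ratio is 0.099 and the power 53.9%.

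With an assumed 50% (TAU) versus 35% (PIT) in custody and n = 132; the last column uses n = 132 × (1 − r):

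| Released, each arm | Recorded TAU v PIT | Difference (points) | Risk ratio | Power, release recorded as not on ACCT | Power, women in custody only |
|---|---|---|---|---|---|
| 0% | 50.0% v 35.0% | 15.0 | 0.70 | 69.5% | 69.5% |
| 10% | 45.0% v 31.5% | 13.5 | 0.70 | 61.8% | 64.9% |
| 20% | 40.0% v 28.0% | 12.0 | 0.70 | 53.9% | 59.8% |
| 40% | 30.0% v 21.0% | 9.0 | 0.70 | 38.8% | 48.0% |

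Other assumed proportions, at 0%, 20% and 40% released:

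- 40% v 25%: recorded difference 15, 12 and 9 points; power 74.2%, 60.5% and 45.4% (in custody only: 74.2%, 64.5% and 52.2%).
- 60% v 40%: recorded difference 20, 16 and 12 points; power 90.6%, 75.9% and 56.7% (in custody only: 90.6%, 83.3% and 71.5%).

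**No true effect.** Take 40% on an ACCT in custody in both arms.

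- Release 20% in both: 0.40 × 0.80 in each arm, difference 0.
- Release 20% TAU, 30% PIT: 0.40 × 0.70 − 0.40 × 0.80 = 0.28 − 0.32 = −4 points.
- Release 10% TAU, 30% PIT: 0.28 − 0.36 = −8 points.

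**Baseline status.** The entry criterion is true both for a woman with an open ACCT and for one whose ACCT closed within 8 weeks, so a yes to it does not tell them apart. No listed baseline item supplies the missing distinction.

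**The case against.** The case for leaving this alone has real strength.

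- A reader might infer that release will be scored as recovery. No section says so. The ACCT Status Form is not shown and may have a not-applicable option. The Statistical analysis plan section uses available data under missing at random, so a released woman could equally be treated as missing. The handling rule may also sit in a separate SAP. This stands. What remains is that the form is described only as recording participation or not, and that a missing-at-random assumption fits poorly when the state does not exist outside prison. An SAP can set the rule, but it depends on the fields having been collected.
- A reader might infer that the ACCT objective cannot be answered. That does not follow. The worded objective is at 8 weeks, the period the custody criterion is meant to cover, and a randomised comparison of follow-up status is valid without a baseline value. This stands in full.
- The Baseline data list describes an interview, so its silence on a records item proves little, and eligibility information does enter the CTU database. This stands in part: the criterion, as worded, still does not separate open from closed.
- The release and ACCT rates are all assumed, equal release creates no false effect, and a chance imbalance in release is sampling variation that the confidence interval reflects. This stands. The expected harm is dilution and lost power on a secondary outcome for which no power is claimed.

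**Conclusion.** The point holds as a gap in data collection for one secondary outcome; the primary outcome is untouched. The protocol records a custody-only state at a visit beyond its custody requirement and does not stop release from being recorded in the same way as a closed ACCT. If that happened with equal release, the absolute 12-week difference would shrink by the factor (1 − release share), from 15 points to 12 at 20% release and to 9 at 40%, with the risk ratio unchanged. A false difference would need unequal release, for which the documents give no evidence. These sizes rest on assumed ACCT and release rates.

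The absence of a separate baseline status costs precision and makes the result harder to interpret, but it does not invalidate the comparison. The 8-week objective can be answered as worded.

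**What to change.** 1. Record ACCT open or closed at baseline on the Eligibility Form or the NOMIS Baseline Record Sheet, from the ACCT records already read at screening, and adjust the ACCT analysis for it.
2. Add a not-in-custody code to the ACCT Status Form. Analyse ACCT status among women in custody at the assessment and report release by arm. Being in custody is itself determined after randomisation, so the release figures are needed to read the comparison.
3. Reconcile the objective (8 weeks) with the outcome text and the Table of outcomes (8 and 12 weeks), and name 8 weeks as the main ACCT comparison.

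The cost is two form fields, a few minutes of extraction per woman and a short amendment. Restricting the analysis to women in custody reduces the number analysed; in the example above, power at 20% release is 59.8%, against 53.9% if release is recorded as not on an ACCT.

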An opportunity sample of 264 women will be recruited to the research. The sample size is powered to detect a minimal important clinical difference of 33% reduction in self-harm incidents over 8 weeks. This clinically significant difference is based on Hawton et al's systematic review of the efficacy of psychological and pharmacological interventions designed to reduce self-harm repetition [43]. From MOJ prison data, the average number of self-harm episodes over 8 weeks in the control group was 6.65 [3]. We modelled this with a Poisson distribution (mean and variance=6.65) and used Monte Carlo simulations with 1000 simulations to estimate the power for a range of sample sizes, with power defined as the proportion of estimated p-values less than 0.05 for null hypothesis testing (treatment effect is 0), against an alternative hypothesis (33% reduction in the log of the outcome). With 5% significance, to obtain 90% power, we will require 105 per group for the primary analyses. Based on WORSHIP II [6] we estimate 20% attrition so will recruit 132 per group at baseline. This level of attrition is not expected in the primary outcome, due to availability of prison data and the fact that self-reported incidents will be measured on a weekly basis, but allows for attrition in the secondary outcomes.

We expect that there will be several potential therapists because we are using trainees as well as qualified professionals. This means that each therapist will see a small number of participants each (mean≈6.6). In turn, we expect that the ICC will be small (though no estimates are available to inform our calculations), and since the number of participants per cluster is also small, the corresponding design effect indicates a small increase to the sample size would be required to take into account this clustering. We anticipate that this will be balanced by accounting for baseline prognostic factors in our statistical models, and that 90% power will be maintained with lower than 20% attrition rate for the primary outcome. We shall include a random effect for each therapist within the statistical analysis models.

Planned recruitment rate

The predicted figures have been calculated based on the number of women who will pass through each of the prisons, depending on their size and the recruitment rate achieved in WORSHIP II. The predicted figures (confirmed by HMPPS) are calculated as follows:

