Analyses of the quantitative data will use an intention-to-treat (ITT) approach with analysis of randomised participants, regardless of non-compliance with protocol. Analyses will post-date final follow-up assessments, with consideration of potential biases from loss to follow-up. The primary outcome (number of incidents of self-harm at 8 weeks) will be analysed using a mixed Poisson model that adjusts for pre-specified baseline covariates and includes a random effect for therapist (since there are multiple therapists per site).

Secondary outcomes will be analysed using a linear mixed model over all repeated measures. Time will be included as a categorical factor, as well as a time*treatment interaction. We will estimate the effect at 8 and 12 weeks separately and report these as an adjusted mean difference.

WORSHIP III	IRAS No: 241606

We can explore possible subgroup effects (particularly around ethnicity, see above) using a treatment by covariate interaction in the fixed part of the model. We are not powered to detect significant interactions and are not currently pre-specifying any potential subgroups.

As secondary analyses, we shall explore a dose-response relationship using randomisation as an instrumental variable for number of sessions received. If there are significant effects on secondary outcomes which are also potential mechanisms (e.g. hopelessness, self-esteem), we shall perform a mediation analysis to test if these account for any observed treatment effects on the primary outcome using causal mediation approaches.

The sensitivities of all treatment effect estimates to missing outcome data will be explored; these models will explore the robustness of the treatment estimates to whatever small amount of missing data there is. The main analysis will use all available data that we believe are valid under the assumption of missing at random. We shall then use a suite of sensitivity analysis to explore the robustness of the primary analysis to departures from assumptions, including all randomised participants. If required, sensitivity analyses will include multiple imputation, and imputing a range of values for missing data under missing not at random assumptions.

Qualitative Analysis

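### Level of harm is fixed as each woman's average over her own incidents, which has no value for a woman with none and can rise when PIT prevents mainly low-harm incidents

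*Protocol*

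**What the plan says.** The protocol (Outcome measures, Exploratory outcomes) classes each incident as low, medium or high harm. The lowest class still requires an incident: "a low level of harm will be defined as any episode not needing resuscitation or external hospitalisation". There is no class for no incident, and the classes carry no numeric scores. The per-woman summary is then fixed: "For each participant, we shall calculate an average level of harm across all incidents".

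The status of this outcome is not consistent. It stands under Exploratory outcomes in the body, but the Trial Summary lists it with the secondary objectives and measures. The outcome table has it assessed at 8 and 12 weeks.

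ACCT status stands under Secondary outcomes and is a yes/no item: "We will record whether the participant is taking part in the ACCT process at 8-weeks and at 12 weeks". For analysis, the protocol's section headed Statistical analysis plan says: "Secondary outcomes will be analysed using a linear mixed model over all repeated measures". It adds: "We will estimate the effect at 8 and 12 weeks separately and report these as an adjusted mean difference". It makes no exception for a binary outcome. The same section sets an intention-to-treat approach. A separate statistical analysis plan was not available for this review.

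**The concern.** An average over incidents divides by the number of incidents, and that number is the primary outcome. Two things follow.

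First, the average does not exist when the number is zero. If PIT works, more women in PIT than in TAU will be in that position, so the women who have a value are no longer the groups formed by randomisation.

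Second, the average describes the mix of a woman's incidents and not the amount of harm she suffers. Preventing low-harm incidents takes the mild ones out of her average and raises it.

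At stake is a result that reads as greater severity under PIT when no woman has had more serious harm. The levels are also ordinal, so any average depends on scores that the protocol does not give.

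For ACCT status the matter is smaller: by the wording, a 0/1 outcome falls under a model that assumes normal errors with constant variance.

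**Working it through.** The protocol states no figure for harm level or ACCT status, so there is none to reproduce.

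**Inputs from the protocol** (Sample size calculation). The TAU mean: "the average number of self-harm episodes over 8 weeks in the control group was 6.65". The counts are taken as Poisson. The effect: "minimal important clinical difference of 33% reduction in self-harm incidents over 8 weeks". This gives a PIT mean of 6.65 × (1 − 0.33) = 4.4555. The section also words the effect as a reduction in the log of the outcome; the rate reading is used here.

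**Assumptions of this review.** Dispersion k, with variance m + k·m² and k = 0 for Poisson. Scores low = 1, medium = 2, high = 3. A TAU mix of 90% low, 6% medium and 4% high.

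**Step 1: women without an average.** P(0) = exp(−m) for Poisson and (1 + k·m)^(−1/k) otherwise.

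| k | TAU | PIT |
|---|---|---|
| 0 (protocol) | exp(−6.65) = 0.1% | exp(−4.4555) = 1.2% |
| 0.5 | 4.325^(−2) = 5% | 3.228^(−2) = 10% |
| 1 | 1/7.65 = 13% | 1/5.4555 = 18% |
| 2 | 14.3^(−0.5) = 26% | 9.911^(−0.5) = 32% |

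**Step 2: one woman, nobody lost.** Average = (L + 2M + 3H)/(L + M + H).

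- Nine low and one high: (9 + 3)/10 = 1.20.
- Five low and one high: (5 + 3)/6 = 1.33.
- All three counts multiplied by the same factor: the factor cancels and the average does not move.
- Scoring: loss of life is classed as high, so a woman with nine low incidents and a fatal one scores 1.20, below the 2.0 of a woman with a single medium incident.

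**Step 3: whole arms.** If every woman has the same mix, the expected average among women with at least one incident is the mean score of an incident. Counts below are per TAU incident.

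| Scenario | Average | Medium/high per woman |
|---|---|---|
| TAU | 0.90 + 0.12 + 0.12 = 1.14 | 6.65 × 0.10 = 0.665 |
| PIT prevents low only | (0.57 + 0.12 + 0.12)/0.67 = 1.21 | 0.665 |
| PIT: low −35%, medium/high −15% | (0.585 + 0.102 + 0.102)/0.67 = 1.18 | 0.665 × 0.85 = 0.565 |
| PIT: all levels −33% | 0.67 × 1.14/0.67 = 1.14 | 0.665 × 0.67 = 0.446 |

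In the third row serious incidents fall and the average still rises. Simulation of the per-woman average gave the same values at k = 0, 0.72 and 2, so this effect does not need overdispersion.

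**Step 4: selection alone.** Let half the women have mean 2 with all incidents low, and half have mean 11.3 with 20% high (overall mean 6.65), and cut every rate by 33%. The share without a value is 7% in TAU and 13% in PIT. The average rises from about 1.21 to 1.23 because low-rate women leave it. So with unequal mixes a uniform benefit can also move it, though only slightly here.

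**Step 5: ACCT status.** The mean difference of a 0/1 variable is a risk difference. In simulation, an unadjusted linear comparison with 105 women per arm had type I error of 4.4%, 5.1% and 4.5% at ACCT proportions of 0.5, 0.2 and 0.05.

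**The case against.** The body of the protocol labels this outcome exploratory, and no primary conclusion or sample size rests on it. It would be read beside the incident count, and deaths, life-threatening events and hospital admissions are reported separately as serious adverse events. Under the protocol's own Poisson model almost every woman has at least one incident. The scores, the mix and k are assumptions. A rule for women with no incidents may stand in a separate analysis plan.

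Most of this limits the weight of the point without removing it. A zero rule would not repair the average: scoring 0 for no incident, the low-only scenario under Poisson still gives 1.209 × (1 − 0.0116) = 1.19 in PIT against 1.14 in TAU. The average is also a stated choice, not a detail left open.

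Four stronger readings are tempting and are not supported:

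- **That the protocol drops the women who respond best.** It gives no rule for them in either direction.
- **That half or more of the women would lack a value.** The Background rate of 1987 incidents per 1000 women a year gives 1.987 × 8/52 = 0.306 per woman. Assigned wholly to the one third who self-harm, that is 0.92. With k = 1 it would leave 1/1.917 = 52% of TAU and 1/1.614 = 62% of PIT without an average. But the planning mean is 6.65, entry requires self-harm in the last month, and both the assignment to one third and k = 1 are assumptions.
- **That the average will rise under PIT.** It can, if low-harm incidents are prevented more than serious ones. The protocol does not say which incidents PIT would prevent.
- **That the ACCT result will mislead.** None of the checks shows it. The objection there is to model form only: normal errors, and fitted values that can leave the 0 to 1 range.

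**Conclusion.** The point holds for level of harm. As fixed, the average is undefined for a woman with no incidents, its analysis set depends on a treatment-affected outcome, and its direction need not follow benefit.

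The loss of women is negligible on the protocol's Poisson assumption and becomes material only if counts are overdispersed. The reversal of direction needs no overdispersion and no loss. It depends on a change in the mix of incidents, and its size (for example 1.14 to 1.21) depends on the assumed scores and mix.

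This merits a change of wording before analysis. It does not threaten the primary result. The ACCT part is a minor wording point.

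**What to change.** Replace the average with an outcome that exists for every randomised woman with incident data. Either of these serves:

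- the number of medium- or high-harm incidents over 8 and over 12 weeks, analysed with a count model; or
- the worst level reached in each period, with 0 for no incident, analysed with an ordinal model.

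If the average is kept as description, report beside it the number of women in each arm who have no value. Label the outcome as secondary or exploratory consistently in the Trial Summary and the body.

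For ACCT status, name a model for a binary outcome at 8 and 12 weeks and report a risk difference or odds ratio.

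The cost is protocol or analysis-plan wording, since the data are already to be collected. The drawback is precision: medium- and high-harm incidents may be rare, so intervals will be wide.
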